## 5.6 Concomitant Medications

Medications taken in the month prior to randomization (Part 1) or arm assignment (Part 2) should be recorded on the baseline case report form. This includes prescription medications, over-the-counter medications, injected medications, biological products, blood products, imported drugs, or street drugs. Participants should be maintained on drugs that they were taking prior to entry unless a change in regimen is medically indicated.

- 5.6.1 Non-permitted medications or treatments (within 30 d of study treatment)
  - 5.6.1.1 Systemic cytotoxic chemotherapy
  - 5.6.1.2 Interferon therapy (e.g. Intron-A®)
  - 5.6.1.3 Radiation therapy
  - 5.6.1.4 Nitrosureas
  - 5.6.1.5 Allergy desensitization injections
  - 5.6.1.6 Systemic corticosteroids, administered parenterally or orally. Inhaled steroids (e.g. Advair®, Flovent®, Azmacort®) are not permitted.
  - 5.6.1.7 Growth factors (e.g. Procrit®, Aranesp®, Neulasta®)
  - 5.6.1.8 Interleukins (e.g. Proleukin®)
  - 5.6.1.9 Other investigational medications

- 5.6.1.10 Street drugs
- 5.6.1.11 Antibodies to CTLA-4, PD-1, PD-L1, or CD137
- 5.6.1.12 Targeted molecular therapy (e.g. vemurafenib, other inhibitor of mutant BRAF, MEK, or cKit).

## 5.6.2 Permitted medications or treatments

- 5.6.2.1 Nonsteroidal anti-inflammatory agents
- 5.6.2.2 Anti-histamines (e.g. Claritin®, Allegra®)
- 5.6.2.3 Topical corticosteroids are acceptable, including steroids with very low solubility administered nasally for local effects only (e.g. Nasonex®).
- 5.6.2.4 Short-term therapy for acute conditions not specifically related to melanoma (except those listed under Section 5.6.1)
- 5.6.2.5 Chronic medications except those listed in Section 4.2.7 or 5.6.1.
- 5.6.2.6 Vaccines, including live vaccines (e.g. FluMist) are permitted, but should be administered at least 2 weeks prior to or at least 2 weeks after a study vaccine.
- 5.6.2.7 Topical forms of chemotherapeutic reagents (e.g. Efudex®) are permitted, but should be administered at least 2 weeks after a study vaccine.

# 6.0 CLINICAL AND LABORATORY EVALUATION

#### 6.1 Screening

The following studies should be completed within 6 weeks prior to randomization unless otherwise noted:

- 6.1.1 Class I HLA-typing (any time prior to randomization; typing for HLA-A and HLA-B is sufficient). If the patient is known to express HLA-A1, A2, or A3, HLA-B testing is not required).
- 6.1.2 Review of pathology at the treating and participating institution (any time prior to randomization). Central pathology review at UVA is not required for pathology reviewed at other participating institutions.
- 6.1.3 CBC with differential, including automated lymphocyte count if available (0.3 ml)
- 6.1.4 Comprehensive chemistry panel to include sodium, potassium, creatinine, fasting glucose, calcium, total bilirubin, AST, ALT, and alkaline phosphatase. NOTE: fasting blood sugars may be evaluated 4h or more after last eating (0.9 ml)
- 6.1.5 Lactate Dehydrogenase (LDH) (0.3 ml)
- 6.1.6 Urinalysis
- 6.1.7 β-HCG for women of childbearing potential (within two weeks prior to randomization)

Version Date: 07-31-17

- 6.1.8 HgB-A1C (only required at baseline)
- 6.1.9 HIV and HCV screening (within 6 months prior to randomization)
- 6.1.10 Chest x-ray or chest CT, abdominal and pelvic CT, and head CT or MRI. PET/CT fusion scan may replace scans of the chest, abdomen, and pelvis.
- 6.1.11 Complete history and physical examination, including:
  - Vital signs
  - Weight
  - Performance Status
  - Assessment of skin and nodal basins for evidence of disease recurrence or metastasis
  - Designation of vaccination sites
  - Medication review

# 6.2 Treatment

The following evaluations will be performed on an outpatient basis on each of the listed days. Blood for these evaluations should be obtained prior to the vaccine injection if a vaccine is scheduled to be administered. Results of those tests are not required prior to administering the vaccine on that date.

## 6.2.1 Day 1

- Interval history and physical examination directed at new signs and symptoms.
- Vital signs
- Weight
- Performance status
- Visual acuity exam using a Snellen chart, and color vision exam using an Ishihara eye chart
- Neurologic function, general.
- Note hair and eve color
- Assessment of skin for vitiligo
- Anti-nuclear antibody and rheumatoid factor (4 ml total)
- Baseline symptoms, codable in the NIH CTCAE v.4.03, to be recorded as preexisting conditions unrelated to the research protocol interventions
- Distribute participant toxicity diary
- Medication review
- Blood collection for immunologic testing: The following blood samples for research will be provided to UVA and processed by the UVA BTRF and stored by the UVA-HITC IML:
  - 120 cc blood collected in heparinized green top tubes for lymphocytes. This may be decreased to 100 cc if more blood must be drawn for safety or screening labs, in order to comply with institutional limits on total blood drawn in a day.
  - 20 cc blood collected in red top tubes for serum.
- Vaccine administration

# 6.2.2 Day 8

 Interval history and physical examination directed at new signs and symptoms. Examination of the vaccine site(s) should be included..

Version Date: 07-31-17

- Vital signs
- Weight
- Performance status
- Review of adverse events
- Review of participant toxicity diary and distribute new toxicity diary
- Medication review
- Blood collection for immunologic testing:\_The following blood samples for research will be provided to UVA and processed by the UVA BTRF and stored by the UVA-HITC IML:
  - 80 cc blood collected in heparinized green top tubes for lymphocytes.
  - 20 cc blood collected in red top tubes for serum
- Biopsies of 1st vaccine site (all patients), and biopsies of normal skin (patients 1-6 only in Part 1). Details in section 5.4.6 and in Study Manual.
- Vaccine administration

## 6.2.3 Day 15

- Interval history and physical examination directed at new signs and symptoms. Examination of the vaccine site(s) should be included.
- Vital signs
- Weight
- Performance status
- Review of adverse events
- Review of participant diary and distribute new toxicity diary
- Medication review
- Vaccine administration

## 6.2.4 Day 22

- Interval history and physical examination directed at new signs and symptoms. Examination of the vaccine site(s) should be included.
- Vital signs
- Weight
- Performance status
- Review of adverse events
- CBC with differential, including automated lymphocyte count if available (0.3 ml)
- Comprehensive chemistry panel to include sodium, potassium, creatinine, glucose, calcium, total bilirubin, AST, ALT, and alkaline phosphatase. (0.9 ml)
- Lactate Dehydrogenase (LDH) (0.3 ml)
- Anti-nuclear antibody and rheumatoid factor (4 ml total)
- Assessment of skin for vitiligo
- Neurologic function
- Vaccine Site Biopsy (3)
- Review of participant diary and distribute new toxicity diary
- Medication review

- Blood collection for immunologic testing:\_The following blood samples for research will be provided to UVA and processed by the UVA BTRF and stored by the UVA-HITC IML:
- 80 cc blood collected in heparinized green top tubes for lymphocytes.
- 20 cc blood collected in red top tubes for serum
- Biopsies of 3rd vaccine site (all patients), and biopsies of normal skin (patients 1-6 only, in Part 1). Details in section 5.4.6 and in Study Manual.

#### 6.2.5 Day 36

- Interval history and physical examination directed at new signs and symptoms. Examination of the vaccine site(s) should be included.
- Vital signs
- Weight
- Performance status
- Review of adverse events
- Review of participant diary and distribute new toxicity diary
- Medication review
- Vaccine administration

# 6.2.6 Day 43

- Interval history and physical examination directed at new signs and symptoms. Examination of the vaccine site(s) should be included.
- Vital signs
- Weight
- Performance status
- Review of adverse events
- Review of participant diary and distribute new toxicity diary
- Medication review
- Blood collection for immunologic testing: The following blood samples for research will be provided to UVA and processed by the UVA BTRF and stored by the UVA-HITC IML:
  - $\circ$  80 cc blood collected in heparinized green top tubes for lymphocytes.
  - 20 cc blood collected in red top tubes for serum

# 6.2.7 Day 57

- Interval history and physical examination directed at new signs and symptoms. Examination of the vaccine site(s) should be included.
- Vital signs
- Weight
- Performance status
- Review of adverse events
- Review of participant diary and distribute new toxicity diary
- Medication review
- Vaccine administration

# 6.2.8 Day 78

- Interval history and physical examination directed at new signs and symptoms. Examination of the vaccine site(s) should be included.
- Vital signs
- Weight
- Performance status
- Review of adverse events
- CBC with differential, including automated lymphocyte count if available (0.3 ml)
- Comprehensive chemistry panel to include sodium, potassium, creatinine, glucose, calcium, total bilirubin, AST, ALT, and alkaline phosphatase. (0.9 ml)
- Lactate Dehydrogenase (LDH) (0.3 ml)
- Anti-nuclear antibody and rheumatoid factor (4 ml total)
- Review of participant diary and distribute new toxicity diary
- Medication review
- Vaccine administration

## 6.2.9 Day 85

- Interval history and physical examination directed at new signs and symptoms. Examination of the vaccine site(s) should be included.
- Vital signs
- Weight
- Performance status
- Review of adverse events
- CBC with differential, including automated lymphocyte count if available (0.3 ml)
- Comprehensive chemistry panel to include sodium, potassium, creatinine, glucose, calcium, total bilirubin, AST, ALT, and alkaline phosphatase. (0.9 ml)
- Lactate Dehydrogenase (LDH) (0.3 ml)
- Chest X-ray or chest CT
- Visual acuity exam using a Snellen chart, and color vision exam using an Ishihara eye chart
- Neurologic function
- Note hair and eye color
- Assessment of skin for vitiligo
- Review of participant diary
- Medication review
- Blood collection for immunologic testing:\_The following blood samples for research will be provided to UVA and processed by the UVA BTRF and stored by the UVA-HITC IML:
  - 80 cc blood collected in heparinized green top tubes for lymphocytes.
  - o 20 cc blood collected in red top tubes for serum

### 6.2.10 Week 26

 Interval history and physical examination directed at new signs and symptoms. Examination of the vaccine site(s) should be included.

Version Date: 07-31-17

- Vital signs
- Weight
- Performance status
- Anti-nuclear antibody and rheumatoid factor (4 ml total)
- Chest x-ray or chest CT
- Neurologic function
- Assessment of skin for vitiligo
- Medication review
- Blood collection for immunologic testing:\_The following blood samples for research will be provided to UVA and processed by the UVA BTRF and stored by the UVA-HITC IML:
  - o 80 cc blood collected in heparinized green top tubes for lymphocytes.
  - o 20 cc blood collected in red top tubes for serum

## 6.2.11 Weeks 52 and 104 (Year 1 and 2)

- Interval history and physical examination directed at new signs and symptoms. Examination of the vaccine site(s) should be included.
- Vital signs
- Weight
- Performance status
- Medication review
- Blood collection for immunologic testing: The following blood samples for research will be provided to UVA and processed by the UVA BTRF and stored by the UVA-HITC IML:
  - o 80 cc blood collected in heparinized green top tubes for lymphocytes.
  - o 20 cc blood collected in red top tubes for serum

#### 6.3 Tumor tissue collection

If during the study, participants develop metastases or recurrences, these may be removed, and following receipt by pathology, may be evaluated by the study research team. Tissue samples may be screened for antigen expression or protein profiles using tests such as Western blots, immunohistochemistry, PCR, flow cytometry or gene chip analysis. Tumor escape mechanisms may also be evaluated. Specimens will be used in immunological assays to assess T cell function or antibody response. Assays generally used for this type of testing include, but are not limited to, Elspot assays, ElSAs, chromium-release assays, proliferation assays and intracellular cytokine staining. Specimens may be used to study the immunologic aspects of the tumor microenvironment or as targets or controls in laboratory assays. Specimens may be used to establish cell lines for long-term studies.

This tissue may also be compared to lesions resected prior to enrollment, which will be requested from the pathology department of each institution as paraffin-embedded tissue samples, and these tissues may be banked for use in future studies. If participants are removed from the study or progress during or after follow-up, tissue may be collected for use as part of this study, as described above, or banked for use in future studies

# 7.0 REGULATORY AND REPORTING REQUIREMENTS

Adverse event reporting requirements for this trial, as specified in this section, apply to patients accrued at all participating sites. There will be accrual at UVA and at MD Anderson

Version Date: 07-31-17

Cancer Center; UVA will be the coordinating site, and responsibility for data coordination and reporting for the study as a whole falls to the Human Immune Therapy Center (HITC). Throughout this section, when referring to 'Cancer Center Database', 'Cancer Center DSMC', 'CRC', 'Pl' or, 'nurse practitioner', they are preceded by 'site' when it refers to reporting within either of the participating institutions, or are preceded by 'UVA' when it refers to central reporting to the coordinating UVA center.

In addition to the reporting requirements for the study, specified in this section of the protocol, investigators should also follow their institutional policy for documentation in their database and reporting to the IRB locally at their own site.

### 7.1 Definitions

#### 7.1.1 Adverse event (AE) –

Any unfavorable and unintended sign (including an abnormal laboratory finding), symptom, or disease temporally associated with the use of a medical treatment or procedure regardless of whether it is considered related to the medical treatment or procedure (attribution of unrelated, unlikely, possible, probable, or definite). Medical conditions or diseases present before starting the investigational drug will be considered as treatment-related AEs if they worsen after starting study treatment.

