#### 7.2 Attribution Assessment

7.2.1 Attribution – The determination of whether an adverse event is related to a medical treatment or procedure. The attribution groups are:

Definite – Applies to those adverse events which, the investigator feels are incontrovertibly related to the vaccine. An adverse event may be assigned an attribution of definitely related if or when (must have all of the following):

- It follows a reasonable temporal sequence from administration of the test drug.
- It could not be reasonably explained by the known characteristics of the subject's clinical state, environmental or toxic factors, or other modes of therapy administered to the subject.
- It disappears or decreases on cessation or reduction in dose with re-exposure to drug. (Note: This is not to be constructed as requiring re-exposure of the subject; however, the group of definitely related can only be used when a recurrence is observed.)
- It follows a known pattern of response to the test drug.

Probable – Applies to those adverse events for which, after careful consideration at the time they are evaluated, are felt with a high degree of certainty to be related to the test drug. An adverse event may be considered probably related if or when (must have three of the following):

• It follows a reasonable temporal sequence from administration

Version Date: 07-31-17

of the test drug.

- It could not be reasonably explained by the known characteristics of the subject's clinical state, environmental or toxic factors, or other modes of therapy administered to the subject.
- It disappears or decreases on cessation or reduction in dose.
  There are important exceptions when an adverse event does
  not disappear upon discontinuation of the drug, yet drugrelatedness clearly exists (e.g. bone marrow depression, fixed
  drug eruptions, tardive dyskinesia).
- It follows a known pattern of response to the test drug.

Possible – Applies to those adverse events for which, after careful consideration at the time they are evaluated, a connection with the test drug administration appears unlikely but cannot be ruled out with certainty. An adverse event may be considered possibly related if or when (must have two of the following):

- It follows a reasonable temporal sequence from administration of the test drug.

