- It could not readily have been produced by the subject's clinical state, environmental or toxic factors, or other modes of therapy administered to the subject.
- It follows a known pattern of response to the test drug.

Unlikely – Applies to those adverse events for which, after careful consideration at the time they are evaluated, are judged to be unrelated to the test drug. An adverse event may be considered unlikely if or when (must have two of the following):

- It does not follow a reasonable temporal sequence from administration of the test drug.
- It could readily have been produced by the subject's clinical state, environmental or toxic factors, or other modes of therapy administered to the subject.
- It does not follow a known pattern of response to the test drug.
- It does not reappear or worsen when the drug is readministered.

Unrelated – Applies to those adverse events, which after careful consideration, are clearly and incontrovertibly due to extraneous causes (disease, environment, etc.).

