## The process of reporting AEs will occur as follows:

- A. Identify the type of event using the NCI CTCAE v4.03 (Appendix 6). The CTCAE provides descriptive terminology and a grading scale for each adverse event listed.
- B. Grade the event using the NCI CTCAE v4.03.
- C. Determine whether the AE is related to the vaccine. Attribution groups are defined in Section 7.2.1.
- D. Determine the prior experience of the AE. Expected events are those that have been previously identified as resulting from administration of the vaccine. An AE is expected when it is listed in Section 7.4.3.
- E. Determine the adverse event classification of the AE, as specified and defined in Section 7.5.
- F. Determine whether the AE is a dose-limiting toxicity and report as specified below.
- G. Determine whether the AE is an SAE and report as specified below.
- H. AEs determined to require expedited reporting to the Sponsor, UVA HITC, must also be reported to your own institution according to the local policy and procedures.

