# 7.8 Adverse Event Stopping Guidelines

Based on results from previous vaccinations with 12-MP and tetanus peptide preparations, and with findings from use of resiquimod and polyICLC, significant toxicity is not anticipated. The study will be monitored continuously for treatment-related adverse events within each vaccine preparation by the sponsor. Data from the UVA- Mel44 vaccine trial (Arm A) (using 12-MP and tetanus peptide) indicate an 8% rate of treatment-related unexpected Grade 3 adverse events.

Version Date: 07-31-17

Adverse events will be described and coded based upon the NCI CTCAE v4.03.

A DLT is defined as any unexpected adverse event that is possibly, probably or definitely related and:

- ≥ Grade 3, with the exception of grade 3 injection site reaction with ulceration ≤ 2 cm
- ≥ Grade 1 ocular adverse events as defined under Section 7.5
- ≥ Grade 2 allergic/autoimmune reactions

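### Section 7.1.1 labels every worsening pre-existing condition treatment-related, in conflict with the attribution rules in 7.2 and 7.6.1, and can lead to over-counted DLTs

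*Combined protocol and SAP*

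**What the plan says.** Section 7.1.1 contains two sentences that do not fit together. The first counts an event as an adverse event "regardless of whether it is considered related to the medical treatment or procedure (attribution of unrelated, unlikely, possible, probable, or definite"), so the definition takes no position on cause. The second says that conditions which predate study drug "will be considered as treatment-related AEs if they worsen after starting study treatment". It has no causality test, no exception and no reference to Section 7.2.

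Other sections treat relatedness as a judgement:

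- Section 7.2 defines attribution as "The determination of whether an adverse event is related to a medical treatment or procedure" and gives criteria for each category. One criterion for Unlikely is "It could readily have been produced by the subject's clinical state, environmental or toxic factors, or other modes of therapy administered to the subject".
- Section 7.6.1, step C, instructs: "Determine whether the AE is related to the vaccine". DLT status is decided later, at step F.
- Section 6.2.1 has codable baseline symptoms recorded on Day 1, "to be recorded as preexisting conditions unrelated to the research protocol interventions".
- Section 7.8 opens: "A DLT is defined as any unexpected adverse event that is possibly, probably or definitely related and". It then sets thresholds: Grade 3 or higher in general (with an exception for injection site reactions with small ulceration), Grade 1 or higher for the listed ocular events, and Grade 2 or higher for allergic or autoimmune reactions. Section 9.7.1 repeats the attribution categories and refers back to 7.8.

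The phrase treatment-related also appears in the ocular DLT rules of Section 7.5 and in the title of Table 21 (Section 9.6.2), which sets the Part 2 stopping boundary.

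**The concern.** Two careful investigators could classify the same event differently. Take a baseline illness that worsens to Grade 3, is not on the Section 7.4.3 lists, and is readily explained by the participant's clinical state. Under 7.1.1 it is treatment-related because it worsened. Under 7.2 it meets a criterion for Unlikely. No passage gives precedence to either.

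The label matters because several decisions depend on relatedness:

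- the DLT count monitored against Table 21, where two to four events are enough to suspend accrual;
- the DLT proportion reported for safety, which is a primary endpoint, and its comparison with Part 1 Arm E;
- whether an individual's protocol treatment is discontinued, since Section 5.5.2.1 ties this to a DLT (it points to Section 7.4 for the definition, which is in 7.8; that cross-reference also needs reconciling);
- reporting times in Table 12: an unexpected Grade 3 event without hospitalization is entered within 30 days if unrelated or unlikely, but within 7 days if possibly, probably or definitely related.

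**Working it through.** **1. Can the label reach the DLT count?**

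On a literal reading, yes. Section 7.5 makes certain treatment-related ocular events DLTs, and Table 21 counts treatment-related DLTs. Someone who takes the 7.1.1 label as settling relatedness would then apply only the remaining tests. Those tests are real limits: the event must be absent from the 7.4.3 lists (Section 7.1.2), and it must meet a grade or type threshold in 7.8 or 7.5. Someone who follows 7.6.1 step C and then 7.8 would attribute the event first and would not count an unrelated one.

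**2. Reproduce Table 21.**

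Inputs from Section 9.6.2: p0 = 0.05, p1 = 0.30, alpha = 0.05, beta = 0.20. The Wald upper boundary at n participants is the smallest integer at or above

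[ln((1 − beta)/alpha) + n × ln((1 − p0)/(1 − p1))] / ln[p1(1 − p0)/(p0(1 − p1))]

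= [ln 16 + n × ln(0.95/0.70)] / ln(0.285/0.035)

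| n | value | boundary |
|---|---|---|
| 2 | 1.61 | 2 |
| 4 | 1.90 | 2 |
| 5 | 2.05 | 3 |
| 11 | 2.92 | 3 |
| 12 | 3.07 | 4 |
| 18 | 3.94 | 4 |

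All three rows of Table 21 are reproduced exactly. The boundary itself is not in error.

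**3. Illustrate the sensitivity.**

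The documents give no rate for unrelated worsening that would also be unexpected and reach a DLT threshold. Let q be that rate per participant, an assumption, independent of a true related DLT rate of 5%. The counted rate is p = 1 − 0.95 × (1 − q).

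The crossing probability is an exact recursion. After each participant, the probability of k events without a crossing so far is updated as P_n(k) = P_(n−1)(k) × (1 − p) + P_(n−1)(k − 1) × p. Any mass at or above the Table 21 boundary is then removed and added to the crossing probability. The two sample sizes are the target of 16 eligible participants and the maximum of 18 (Section 9.5.2).

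| assumed q | counted rate p | crossing by n = 16 | crossing by n = 18 |
|---|---|---|---|
| 0 | 5.0% | 2.7% | 2.9% |
| 2% | 6.9% | 5.7% | 6.4% |
| 5% | 9.75% | 12.5% | 14.4% |
| 10% | 14.5% | 28.5% | 32.9% |

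The nominal 5% type I error is exceeded once q is about 2%. Adding the rates outright, to counted rates of 10% and 15%, gives 15.2% and 35.1% at n = 18, so the way of combining them changes little.

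**4. The one observed rate.**

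Part 1 Arm E had 1/16 = 6.25% DLTs. If that figure already includes anything counted under the 7.1.1 label, crossing at a total rate of 6.25% is 4.5% by n = 16 and 5.1% by n = 18, close to nominal. The stated 95% interval, 0.2% to 30.2%, is too wide to settle the matter.

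**The case against.** A reader might infer that an unrelated flare becomes a DLT by definition, that Section 7.2 is bypassed, and that the primary safety estimate is therefore inflated. The documents do not support this. Sections 7.8 and 9.7.1 define a DLT by the possibly, probably and definitely categories, which are the 7.2 attribution groups. Treatment-related is not one of those groups, and 7.1.1 does not say which group a worsened condition would receive. Step C of 7.6.1 precedes the DLT decision at step F. Section 7.7.1 requires attribution to be noted for every adverse event except Grade 1 hematologic or metabolic ones.

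The route is also narrow. Participants are clinically disease-free with ECOG status 0 or 1, and more serious autoimmune disease is excluded. Any error is conservative. A crossing leads to suspension and review by the study PI, co-investigators and DSMC, where attribution can be examined. The values of q are assumed, and the 2014 and 2017 entries in the summary of changes list no change to 7.1.1, so the Arm E count may already reflect this wording.

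All of this stands and limits the point to a minor one. It does not make the sentence right. The contradiction is explicit, the same label recurs in the ocular rules and in Table 21, and a later review would not clearly restore a discontinued participant's treatment or reclassify a tabulated event while 7.1.1 stands.

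**Conclusion.** The 7.1.1 sentence is wrong as written. It contradicts the definition just before it, the 7.2 criteria and step C of 7.6.1, with no rule of precedence. It permits over-counting of DLTs and shorter reporting times for unrelated events, but does not compel either, because 7.6.1, 7.8 and 9.7.1 keep the attribution test.

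The size of any effect cannot be taken from the documents. The rise in crossing probability by n = 18 from 2.9% to about 6%, 14% or 33% rests on an assumed q of 2%, 5% or 10%, independence, and a true DLT rate of 5%. It shows only that a boundary of two to four events is sensitive to a few misclassified ones. Severity is minor.

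**What to change.** Replace the second sentence of Section 7.1.1 with: *Conditions present before study drug that worsen after starting treatment will be recorded as adverse events, with attribution assigned under Section 7.2.* This brings 7.1.1 into line with 7.2, 7.6.1 and 7.8, and leaves Table 21, the grading and the DLT thresholds unchanged.

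Confirm and record that the Part 1 Arm E count of 1/16 was made on the same attribution basis. If it was not, restate it before comparing it with Part 2.

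The cost is one sentence in the protocol and a check of the Arm E attribution records.
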